## **5.10. Analysis of Immunogenicity Data**

### **5.10.1. Analysis of ADA Data**

The immunogenicity variables described in Section 4.8 will be summarized using descriptive statistics. Immunogenicity will be characterized by ADA responses and titers observed in patients in the ADA analysis set. ADA response categories and titer categories are defined as follows:

#### *ADA response categories*

- ADA Negative, defined as ADA negative response at all time points, regardless of any missing samples.
- Pre-existing immunoreactivity, defined as either an ADA positive response in the ADA assay at baseline with all post first dose ADA results negative, OR a positive response at baseline with all post first dose ADA responses less than 9-fold over baseline titer levels.
- Treatment-emergent response, defined as a positive response in the ADA assay post first dose when baseline results are negative or missing. The treatment-emergent responses will be further characterized as Persistent, Indeterminate or Transient:

- Persistent Response – Treatment-emergent ADA positive response with two or more consecutive ADA positive sampling time points, separated by at least 16-week period (based on nominal sampling time), with no ADA negative samples in between, regardless of any missing samples.
- Indeterminate Response – Treatment-emergent ADA positive response with only the last collected sample positive in the ADA assay, regardless of any missing samples.
- Transient Response – Treatment-emergent ADA positive response that is not considered persistent or indeterminate, regardless of any missing samples.
- Treatment-boosted response, defined as a positive response in the ADA assay post first dose that is greater than or equal to 9-fold over baseline titer levels, when baseline results are positive

*Titer categories (Maximum titer values)*

- Low (titer <1,000)
- Moderate ( $1,000 \leq \text{titer} \leq 10,000$ )
- High (titer >10,000)

The following analysis will be provided:

- Number (n) and percent (%) of ADA-negative patients (pre-existing immunoreactivity or negative in the fasinumab ADA assay at all time points) by treatment groups
- Number (n) and percent (%) of treatment-emergent ADA positive patients by treatment groups and ADA titer categories
  - Number (n) and percent (%) of persistent treatment-emergent ADA positive patients
  - Number (n) and percent (%) of indeterminate treatment-emergent ADA positive patients
  - Number (n) and percent (%) of transient treatment-emergent ADA positive patients
- Number (n) and percent (%) of treatment-boosted ADA positive patients by treatment groups and ADA titer categories

Listing of all ADA titer levels will be provided for patients with pre-existing, treatment-emergent and treatment-boosted ADA response.

**5.10.2. Analysis of Neutralizing Antibody (NAb) Data**

The absolute occurrence (n) and percent of patients (%) with NAb status in the NAb analysis set will be provided by treatment groups.

### **5.10.3. Association of Immunogenicity with Exposure, Safety and Efficacy**

#### **5.10.3.1. Immunogenicity and Exposure**

Potential association between immunogenicity variables and systemic exposure to fasinumab will be explored by treatment groups. Plots of fasinumab concentration may be provided for analyzing the potential impact of ADA response status, titer and NAb on PK.

#### **5.10.3.2. Immunogenicity and Safety and Efficacy**

Potential association between immunogenicity variables and safety may be explored with a primary focus on the following safety events during the TEAE period:

- Injection site reaction (serious or severe and lasting 24 hours or longer)
- Hypersensitivity (SMQ: Hypersensitivity [Narrow])
- Anaphylactic Reaction (SMQ: Anaphylactic Reaction [Narrow])

Potential association between immunogenicity variables and efficacy and safety endpoints may be explored (e.g. scatter plot or spaghetti plot). The above-mentioned safety and efficacy analyses will be conducted using the following categories:

- ADA positive patients, that is patients with treatment-emergent or treatment-boosted response.
- ADA negative patients, that is patients with pre-existing immunoreactivity or negative in the ADA assay at all time points.
- Patients with persistent treatment-emergent ADA response.
- NAb positive patients, that is ADA positive patients who were positive in the NAb assay at any time point analyzed.
- Maximum post-baseline titer in treatment-emergent or treatment-boosted ADA positive patients:
  - Low (titer <1,000)
  - Moderate ( $1,000 \leq \text{titer} \leq 10,000$ )
  - High (titer >10,000)

## 6. DATA CONVENTIONS

The following analysis conventions will be used in the statistical analysis.

### 6.1. Definition of Baseline for Efficacy/Safety Variables

The following baselines will be used for both the efficacy and safety analyses.

- The Year 1 baseline value is defined as the last available value before randomization.
- The Year 2 baseline value is defined as the last available value after the last dose of Year 1 treatment but before the first dose of Year 2 treatment.

### 6.2. Data Handling Convention for Efficacy Variables

#### 6.2.1. Handling of Missing Efficacy Data due to COVID-19 Public Health Measures

Due to public health measures implemented to address the world-wide COVID-19 pandemic, some sites may suspend onsite study visits or patients may opt not to attend. To mitigate data loss, patients may be contacted via telephone and the results of their efficacy measures transcribed verbally and entered into the eCOA devices. For analysis purposes, this data will be treated the same as efficacy data collected in an onsite visit and will be utilized in the efficacy analyses (Bellamy 2002). Sensitivity analysis may be performed excluding data collected via telephone.

### 6.3. Data Handling Convention for Repeat Data

#### Orthostatic Hypotension data

This applies specifically to the data handling of repeat measurements in the assessment of orthostatic hypotension. Per protocol, if the initial vital assessment for orthostatic hypotension is consistent with the definition of orthostatic hypotension, the supine, standing blood pressure or pulse should be repeated up to 2 more times. The guideline for the repeat assessments are shown below:

Initial Assessment	Repeat Assessment 1	Repeat Assessment 2	Does patient meet OH criteria	Value to be used in the analysis
Does not meet OH definition	N/A	N/A	No	Initial Assessment
Meets OH definition - repeat	Does not meet definition – repeat	Does not meet definition	No	N/A
Meets OH definition - repeat	Does not meet definition – repeat	Meets OH definition	Yes, AE of OH reported	Repeat Assessment 2
Meets OH definition - repeat	Meets OH definition	N/A	Yes, AE of OH reported	Repeat Assessment 1

Baseline for the assessment of orthostatic hypotension vital assessments uses the last available assessment prior to the start of study drug. Measurements post-baseline will not be averaged. Rather frequency counts for patients meeting OH criteria for orthostatic hypotension will reflect the scenario as shown on the table.

### **Patient reported outcomes data**

Should there be duplicate entries for patient reported outcomes data (not including diary data), the average of the entries will be used for questionnaires with numerical values such as the WOMAC. The worst category will be used in the analysis for questionnaires with categorical responses such as the SOAS and JPQ.

## **6.4. Data Handling Conventions for Missing Data**

Rules for handling missing data for primary and secondary efficacy variables are described in Section 5.7.1 and Section Section 5.7.3.

### **Handling of Adverse Event and Injection Site Reaction Severity**

If the severity of a TEAE is missing, it will be classified as “severe” in the frequency tables by severity of TEAEs.

### **Handling of Adverse Event Relatedness**

If the assessment of relationship of a TEAE to the study drug or study conduct is missing, it will be classified as “related”.

### **Handling of Adverse Events or Concomitant Medications with missing or partial dates**

*Imputation of AE and Concomitant Missing and Partial start dates:*

Every effort will be made to collect the start dates of all AEs and concomitant medications. However, in the case the start date of an AE or concomitant medication is incomplete or missing, it will be assumed to have occurred on or after the first dose of study medication, except if an incomplete date (e.g., month and year) clearly indicates that the event started prior to treatment. If the partial date indicates the same month or year of the first dose of study medication date, then the start date of the first dose will be imputed, otherwise, the missing day or month by the first day or the first month will be imputed.

*Imputation of Partial AE and concomitant Medication Partial end dates:*

When only year is present, missing AE/concomitant medication end day and month will be imputed to the earlier of (study end date, 31DECYYYY).

When both month and year present, missing AE/concomitant medication end day will be imputed to the last day of the month.

There will be no attempt to impute completely missing AE or concomitant medication end dates. Events with an end date missing will be assumed to be ongoing at the time of data cut off.

### **Handling Missing/Incomplete Medical history dates**

Medical history start dates are used to determine the duration of OA at baseline per eCRF data. Completing missing medical history dates will not imputed. Missing month will be imputed to January and missing day will be imputed to the first day of the month.

### **Handling of Adverse Events classification with missing or partial date/time of first study drug administration**

When the date and time of first study drug dose is missing, the date of randomization will be used as the start date for classification of AEs.

When the time of the first study treatment dose is missing, all AEs that occurred on the date of the first study drug dose will be considered as TEAEs.

### **Handling of missing item data on questionnaires**

#### *WOMAC*

WOMAC scores will be computed when one pain, one stiffness, or 1-3 physical function items are missing. The missing items will be imputed by the mean of available items within the same subscale. The scores will be set to missing if more items are missing.

#### *SF-36*

The Half-Scale rule will be used to impute missing item responses in the SF-36 subscale scores i.e. a score will be computed if the respondent answers at least 50% of items in that scale. The missing items in the scale will be imputed by the mean of available items rounded to the nearest whole number.

The bodily pain subscale consists of Q7 and Q8 of the instrument. Since Q7 is based on 6pt Likert score and Q8 is based on a 5pt Likert scale and because mean imputation will be meaningless, the bodily pain subscale score will not be imputed if any of the questions making up the scale is missing.

#### *EQ-5D-5L*

Index will be set to missing if any of the 5 dimensions is missing.

### **Laboratory Safety Variables below LLOQ or above ULOQ**

For central laboratory data below the lower limit of quantification (LLOQ), half of the lower limit value (i.e., LLOQ/2) will be used for quantitative analyses.

### **Missing laboratory, ECG, vital sign, physical exam, neurological exam**

No imputations for missing laboratory data, ECG data, vital sign data, physical examination, or neurological examination data will be made.

### **Handling of Potentially Clinically Significant Abnormalities**

If a patient has a missing baseline value, they will be grouped in the category “normal/missing at baseline”.

For PCSAs with 2 conditions, one based on a change from baseline value and the other on a threshold value or a normal range, with the first condition being missing, the PCSA will be based only on the second condition.

For a PCSA defined on a threshold and/or a normal range, this PCSA will be derived using this threshold if the normal range is missing; e.g., for eosinophils the PCSA is  $>0.5$  GIGA/L or  $>ULN$  if  $ULN \geq 0.5$  GIGA/L. When ULN is missing, the value 0.5 should be used.

Measurements flagged as invalid by the laboratory will not be summarized or taken into account in the computation of PCSA values.

### **Date of first/last injection**

Date of first injection is the first non-missing start date of dosing filled in the ‘SC Study drug Injection’ CRF module.

If a patient’s date of the last dose is totally missing or unknown, his/her last visit date in the treatment period will be substituted.

## **6.5. Visit Windows**

By-visit analysis (including laboratory data, vital signs, ECG, ADA) will be summarized by the nominal visit number. Assessments taken outside of protocol allowable windows will be displayed according to the case report form (CRF) assessment recorded by the investigator. For assessments without a nominal visit number such as Unscheduled, End-of-Treatment (EOT), and End-of-Study (EOS)/Early Termination (ET) assessments, a visit number will be assigned based on the actual visit date using the study day analysis window based on the targeted visit study day in Section 10.2 Schedule of Time and Events. The following visit windows will be used to map the unscheduled visits, EOT and EOS /ET visits and eCOA assessments based on the study day:

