**Figure 2: Hypothesis Testing Procedure**

### 5.7.5. Analysis of Other Efficacy Variables

As additional sensitivity analyses, the following efficacy endpoints will be analyzed using the same method as was used for hypotheses  $H_{1,1}$ , and  $H_{2,1}$ :

- Change in WOMAC pain subscale scores from baseline to week 48
- Change in WOMAC physical function subscale scores from baseline to week 48
- Change in WOMAC pain subscale scores from baseline to week 52
- Change in WOMAC physical function subscale scores from baseline to week 52

The same analysis used for hypotheses  $H_{1,3}$ ,  $H_{1,16}$ , and  $H_{2,3}$  will be used to analyze the following additional efficacy endpoints:

- The number and percentage of patients with an improvement of  $\geq 50\%$  from baseline in the WOMAC pain subscale scores at weeks 16, 44, 52
- The number and percentage of patients with an improvement of  $\geq 70\%$  from baseline in the WOMAC pain subscale scores at week 16, 44, 52
- The number and percentage of patients with an improvement of  $\geq 30\%$  from baseline in the WOMAC physical function subscale scores at week 16, 44, 52
- The number and percentage of patients with an improvement of  $\geq 50\%$  from baseline in the WOMAC physical function subscale scores at week 16, 44, 52
- The number and percentage of patients with an improvement of  $\geq 70\%$  from baseline in the WOMAC physical function subscale scores at week 16, 44, 52
- The number and percentage of patients meeting the OMERACT-OARSI criterion at week 16, 44, 52

Cumulative distribution of percent change from baseline to Week 16 in the WOMAC pain and physical function scores will be presented by treatment group. The cumulative distribution plot displays a continuous plot of the percent change from baseline on the X-axis and the percent of patients experiencing that change on the Y-axis.

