**Table 1: Year 1 Analysis Windows**

Visit Number	Visit Name	Targeted Study Daysa	Analysis Window in Study Days
1	Screen	Day -30 to Day -11	[-30, -11]
2	Pre-randomization	Day -10 to -7	[-10, -1]
3	Baseline	1	1
Phone 1	Week 1	8	[2, 11]
4	Week 2	15	[12, 22]
5	Week 4	29	[23, 43]
6	Week 8	57	[44, 71]
7	Week 12	85	[72, 99]
8	Week 16	113	[100, 127]
9	Week 20	141	[128, 155]
10	Week 24	169	[156, 183]
11	Week 28	197	[184, 211]
12	Week 32	225	[212, 239]
13	Week 36	253	[240, 267]
14	Week 40	281	[268, 295]
15	Week 44	309	[296, 323]

Visit Number	Visit Name	Targeted Study Days a	Analysis Window in Study Days
16	Week 48	337	[324, 351]
17	Week 52	365	[352, 393]
18	Week 56	393	[394, 463]
19	Week 72	505	[464, 603]
Phone 2	Week 100	701	≥ 604

a Study days are calculated from the first dose of study drug (Day 1).

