**Table 2: Year 2 Analysis Windows**

Visit Number	Visit Name	Targeted Study Days a	Analysis Window in Study Days
17E	Week 52E	365E	[352, 379]
18E	Week 56E	393E	[380, 407]
19E	Week 60E	421E	[408, 435]
20E	Week 64E	449E	[436, 463]
21E	Week 68E	477E	[464, 491]
22E	Week 72E	505E	[492, 519]
23E	Week 76E	533E	[520, 547]
24E	Week 80E	561E	[548, 575]
25E	Week 84E	589E	[576, 603]
26E	Week 88E	617E	[604, 631]
27E	Week 92E	645E	[632, 659]
28E	Week 96E	673E	[660, 687]
29E	Week 100E	701E	[688, 715]
30E	Week 104E	729E	[716, 743]
31E	Week 108E	757E	[744, 813]
32E	Week 124E	869E	[814, 967]
Phone 2E	Week 152E	1065E	≥ 968

a Study days are calculated from the first dose of study drug (Day 1).

If multiple measurements occur within the same visit window, the following rules will be used to determine the analysis value:

- When multiple valid measurements occur within the same visit window, the one closest to the target study day will be used in the analysis.

- When multiple valid measurements occur within equal distance from the target study day, the value after the target study day will be used in the analysis.

Both scheduled and unscheduled measurements will be considered for determining abnormal/PCSV values from laboratory, vital sign or ECG as well as the baseline values.

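### SAP Table 1 sets two Year 1 boundaries after Week 52 14 days late, so Week 56's target day falls in the Week 52 window and about half of on-schedule Week 56 scores are labelled Week 52

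*SAP*

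**What the plan says.** SAP Section 6.5 keeps scheduled safety data on their recorded visit: "By-visit analysis (including laboratory data, vital signs, ECG, ADA) will be summarized by the nominal visit number". Assessments with no nominal visit are assigned one "using the study day analysis window based on the targeted visit study day in Section 10.2 Schedule of Time and Events". The last sentence before Table 1 widens the scope to electronic outcome data: the "visit windows will be used to map the unscheduled visits, EOT and EOS /ET visits and eCOA assessments based on the study day".

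WOMAC and PGA fall under that sentence. Protocol Section 11.2 lists electronic outcome systems for patient-reported data, and SAP Section 6.2.1 has even telephone-collected scores handled this way, with "the results of their efficacy measures transcribed verbally and entered into the eCOA devices".

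Table 1 (Year 1) gives:

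- Week 52, target day 365: days 352–393
- Week 56, target day 393: days 394–463
- Week 72, target day 505: days 464–603
- Week 100 phone call, target day 701: day 604 onward

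Table 2 (Year 2) gives the same target day 365, as Week 52E, the window 352–379. If several valid values fall in one window, "the one closest to the target study day will be used in the analysis".

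SAP Section 5.7.5 uses Week 52 scores, for example "Change in WOMAC pain subscale scores from baseline to week 52". It also uses Week 52 for pain and function responder rates and for the OMERACT-OARSI criterion.

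**The concern.** A window built around a target day should contain that day. Week 56's does not: it starts one day after its own target, and the target is the last day of the preceding visit's window.

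The two visits are not interchangeable. Under the Year 1 schedule the last SC injection is at Week 48 and oral drug is last dispensed then, to cover the period to Week 52. Week 56 is a follow-up visit off both drugs. Labelling its scores Week 52 mixes off-treatment data into an end-of-treatment time point.

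Week 52 is also where gaps were expected. The rationale for Amendment 7 says that COVID-19 would probably push missing Week 52 efficacy data above the original assumption. A follow-up score is therefore most likely to stand in for Week 52 at the visit where missing data were already a known problem.

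**Working it through.** **Inputs.** Target days and windows are from SAP Tables 1 and 2. The permitted Week 56 visit, day 393 ±7, with WOMAC and PGA collected, is from the Year 1 schedule (protocol Table 1, SAP Table 3).

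**Step 1: find the rule behind the windows.** The SAP does not state one, so test the midpoint: upper limit = (target + next target) / 2, rounded down.

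| Boundary | Targets | Midpoint | Stated upper limit | Difference (days) |
|---|---|---|---|---|
| Week 48/52 | 337, 365 | 351 | 351 | 0 |
| Week 52/56 | 365, 393 | 379 | 393 | +14 |
| Week 56/72 | 393, 505 | 449 | 463 | +14 |
| Week 72/100 | 505, 701 | 603 | 603 | 0 |
| Week 52E/56E | 365, 393 | 379 | 379 | 0 |
| Week 108E/124E | 757, 869 | 813 | 813 | 0 |

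From Week 1 on, the midpoint reproduces 15 of 17 boundaries in Table 1 and 16 of 16 in Table 2. The only two misses are adjacent, and both are 14 days late. Week 56 is the only post-baseline visit in either table whose target lies outside its own window.

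**Step 2: slip or choice?** The stated Week 56 window has 463 − 394 + 1 = 70 days. Its Year 2 counterpart, Week 108E (744–813), also has 70. The Week 56 window has the expected length and has been moved as a block by 14 days. A deliberate widening of Week 52 would not have required moving the Week 56/72 boundary as well.

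**Step 3: share of on-schedule Week 56 visits affected.** The permitted days are 393 − 7 = 386 to 393 + 7 = 400, which is 15 days.

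- Days 386–393, 8 of 15 (53%), are labelled Week 52.
- Days 394–400, 7 of 15 (47%), are labelled Week 56.

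The documents give no distribution of visit timing. With discretised normal timing centred on day 393, the share labelled Week 52 is 55% (SD 5 days), 57% (SD 3), 60% (SD 2) or 70% (SD 1). With SD 3 it is 87% if visits centre on day 390 and 22% if they centre on day 396.

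**Step 4: what happens to a relabelled score.**

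- *Week 52 done on schedule (days 358–372).* It is at most 7 days from target. The relabelled Week 56 score is 386 − 365 = 21 to 393 − 365 = 28 days away. The closest-to-target rule keeps the true Week 52 score, and the Week 56 score is lost.
- *Week 52 missing.* The Week 56 score becomes the Week 52 value, though it was taken 386 − 337 = 49 to 393 − 337 = 56 days after the scheduled last injection. In the responder analyses it replaces what would otherwise count as non-response.

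**Step 5: other visits.** Early-termination or unscheduled visits on days 380–393 are labelled Week 52 instead of Week 56. Those on days 450–463 are labelled Week 56 instead of Week 72.

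**Step 6: test the correction.** With limits 379, 449 and 603, all 15 permitted Week 56 days map to Week 56. On-schedule Week 52 (358–372) and Week 72 (498–512) visits keep their labels.

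**The case against.** The arithmetic is hard to dispute. The case on the other side is about reach.

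- *Two boundaries only.* The Week 72/100 limit is right, and the midpoint rule is inferred. This stands as a limit on scope, but the inference rests on 31 of 33 boundaries, and a window that excludes its own target is wrong under any rule.
- *Nominal visits.* Section 6.5 opens with nominal visit numbers and could be read as using windows only for records that lack one. The final sentence names eCOA assessments without that condition, so the literal reading maps scheduled WOMAC and PGA by study day. Even on the narrower reading, unscheduled and early-termination records are still mislabelled.
- *About half.* This depends on when visits took place, as Step 3 shows.
- *Labelled is not analysed.* A follow-up score fills Week 52 only if the patient did not enter Year 2, has no Week 52 score, and attended Week 56 by day 393. Telephone collection reduces the number of such cases, and the documents do not allow their frequency to be estimated. SAP Section 5.7.1 also removes data collected after treatment discontinuation, so in the Week 52 WOMAC change analyses the problem falls mainly on patients who completed treatment and missed that visit.
- *No tested hypothesis uses Week 52.* Co-primary and key secondary endpoints use Week 16, Week 44, or averages over Weeks 4–16 or 36–44, whose windows are all correct. This stands.

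**Conclusion.** The error is real. Two Year 1 boundaries are each 14 days late, Week 56's target day lies in the Week 52 window, and neither document gives a reason. If visits are spread evenly over the permitted days and eCOA data are mapped by study day as Section 6.5 says, 53% of on-schedule Week 56 WOMAC and PGA scores are labelled Week 52. The share exceeds one half for any timing symmetric about day 393, and moves to 22% or 87% if visits centre three days late or early with SD 3.

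The damage falls on the Week 52 change and responder analyses, where Week 52 is missing, and on the Year 1 follow-up WOMAC data, where it is present. SAP Section 7 plans a separate analysis of those follow-up data. Scheduled laboratory, vital-sign, ECG and ADA summaries stay on nominal visits, and the Week 16 and Week 44 endpoints are not directly affected. It should be corrected, but it does not threaten the primary conclusion.

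**What to change.** In SAP Table 1 set:

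- Week 52: 352–379
- Week 56: 380–449
- Week 72: 450–603

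Leave Week 100 at day 604 onward. The cost is three table cells and the matching constants in the programs. No visit, form or other analysis changes.

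If the longer Week 52 window was intended, the SAP should say so, and explain why Week 56 excludes its own target day and why Table 2 treats the same target day differently.
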